The Use of i/t Curve in Assessment of Phototherapy Effects

Study Protocol with SAP

10/21/2015

Study Protocol

Background: Conventional electrodiagnostic examination is useful in daily physiotherapeutic practice. Nevertheless, the subjective assessment of muscle contraction and perceived current vibrations carries the risk of error and thus is a limitation of the method. Therefore, the use of the I/T curve coefficient was proposed in this study. This coefficient is the arithmetic mean of the electrical charge needed to trigger a sensory or motor reaction at different widths of the electrical pulse. PILER (Polychromatic Incoherent Low-Energy Radiation) light affects the sensory and motor excitability of the tissue. The resulting changes may depend on the colour of the filter used in the irradiations. The influence of the colour of polarized light on the condition of excitable tissue has not yet been unambiguously determined, nor have the potential clinical uses of this dependence been defined.

Objective:

- 1. To evaluate changes in neuromuscular excitability occurring after PILER irradiation using filters of different colours.*
- 2. To evaluate the usefulness of the I/T curve coefficient in neuromuscular excitability test.*

Design: Randomized double-blind placebo-controlled trial.

Material and methods.

Participants: 60 healthy volunteers aged 21-23 are assigned to one of four groups: group v (n=15), group x (n=15), group y (n=15), group z (n=15). Group v: irradiation without a filter (white radiation in the entire spectrum and near-infrared radiation; 480-3400 nm)

Group v: irradiation without a filter (white radiation in the entire spectrum and near-infrared radiation; 480-3400 nm)

Group x: irradiation with a red filter (visible red radiation and infrared; 650-800 nm and 800-3900 nm, respectively).

Group y: irradiation with a blue filter (blue radiation; 440-480 nm).

Group z: placebo irradiation (without a filter, 3 min, distance: 100 cm).

PILER light treatment consisted of 10 irradiations to the biceps brachii muscle of the non-dominant limb. Each irradiation lasted 10 minutes, and was performed at a distance of 10 cm. Irradiations were performed every weekday using a Bioptron Pro 1 lamp.

The study was carried out in the Centre for Innovative Research in Medical and Natural Sciences, the University of Rzeszów Faculty of Medicine, Poland

Interventions: Irradiations of the biceps brachii muscle with PILER light. The participants were randomized into 4 groups: group v - no filter/ group x - red filter/ group y - blue filter/ group z – placebo. Muscle examination was carried out before (examination 1) and after (examination 2) the series of PILER light treatments. It included a traditional electrodiagnostic examination and the assessment of the pressure pain threshold (PPT).

Main Outcome Measures: calculating I/T curve coefficient for rectangular (■I/T coeff) and triangular (▲I/T coeff) pulses and the pressure pain threshold (PPT).

SAP:

First, the results in the irradiated group v+x+y (n=45) and the control group z (n=15) were compared to determine differences regarding the sensory excitability parameters and PPT between baseline and outcome measure. The mean, standard deviation and the 95% confidence intervals for were calculated for each parameter. The Mann-Whitney test was used to assess the differences between the irradiated and control groups regarding the changes recorded after irradiation.

Afterwards, comparison was conducted between different filter groups(v, x, y) to determine differences regarding the sensory excitability parameters and PPT between baseline and outcome measure. The mean, standard deviation and the 95% confidence intervals for were calculated for each parameter. The Kruskal-Wallis was used to assess the changes recorded after irradiation in groups with different filter colour (differences between baseline and outcome measure). P values below 0.05 were considered statistically significant.

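### Both planned tests compare unadjusted change and leave examination 1 out as a covariate; adjusting for it is a cheap gain in precision, not the correction of an error

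*Combined protocol and SAP*

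**What the plan says.** Under Interventions, the protocol plans the same two assessments with no group exempted: "Muscle examination was carried out before (examination 1) and after (examination 2) the series of PILER light treatments". Participants are randomised to four groups of 15.

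The SAP then makes two comparisons. In the first, "the results in the irradiated group v+x+y (n=45) and the control group z (n=15) were compared", and the test is specified as "The Mann-Whitney test was used to assess the differences between the irradiated and control groups regarding the changes recorded after irradiation". In the second, across groups v, x and y, "The Kruskal-Wallis was used to assess the changes recorded after irradiation in groups with different filter colour (differences between baseline and outcome measure". The decision rule is "P values below 0.05 were considered statistically significant".

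No baseline covariate or adjusted model appears. For estimates, each of the two SAP paragraphs contains the sentence "The mean, standard deviation and the 95% confidence intervals for were calculated for each parameter", in which the object of the intervals is missing as the text stands. The documents give no pre-post correlation, SD, target effect or power.

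**The concern.** A change score subtracts the whole of the baseline value. That is the most efficient use of baseline only when the regression slope of examination 2 on examination 1 equals 1. If the slope is lower, part of what is subtracted is noise. If it is higher, too little is subtracted. ANCOVA estimates the slope instead of fixing it at 1.

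With 15 per group, any avoidable variance matters. The protocol's first objective is "To evaluate changes in neuromuscular excitability occurring after PILER irradiation using filters of different colours", which calls for estimates of how far the groups differ as well as P values. An adjusted model supplies both from data that are already planned. The stake is precision and power. It is not bias or false-positive error.

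**Working it through.** **Inputs from the documents.** Four groups of 15 (4 x 15 = 60); pooled irradiated group 3 x 15 = 45 against 15; significance at P<0.05, taken as two-sided. The plan has no power or precision figure to reproduce.

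**Assumptions.** Pre-post correlation rho of 0.3, 0.5, 0.7, 0.9; k = post SD/pre SD of 0.8, 1, 1.25; illustrative effects of 0.8 SD. None of these is in the documents.

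**Step 1: validity.** In simulated null trials over this range of rho (normal data, 6,000 per setting), Mann-Whitney rejected in 4.6-5.1% and Kruskal-Wallis in 4.4-4.8%. Both tests hold their level.

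**Step 2: variance.** In units of the baseline variance:

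- Change: 1 + k² − 2k·rho
- ANCOVA residual: k²(1 − rho²)
- Difference: 1 − 2k·rho + k²rho² = (1 − k·rho)²

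The saving is therefore never negative, before the small cost of estimating the slope, and it is zero only when the slope k·rho equals 1. ANCOVA/change variance ratio:

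| k | rho 0.3 | rho 0.5 | rho 0.7 | rho 0.9 |
|---|---|---|---|---|
| 0.8 | 0.50 | 0.57 | 0.63 | 0.61 |
| 1 | 0.65 | 0.75 | 0.85 | 0.95 |
| 1.25 | 0.78 | 0.89 | 0.98 | 0.95 |

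Example: k=1.25, rho=0.7 gives 1.5625 x 0.51 / (1 + 1.5625 − 1.75) = 0.797/0.8125 = 0.98. The slope is 0.875, so little is left to gain. At k=1.25 and rho=0.8 the slope is exactly 1 and the ratio is 1.00.

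Slope estimation costs a little: at k=1, rho 0.5, the saving is about 23% and not 25%.

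**Step 3: interval width at k=1.** The 95% half-width for 45 v 15, in baseline SDs, is t x sqrt(1/45 + 1/15) x sqrt(variance), with 56 df for change and 55 for ANCOVA, ignoring the slope-estimation cost beyond the lost df:

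| | rho 0.3 | rho 0.5 | rho 0.7 | rho 0.9 |
|---|---|---|---|---|
| Change | 0.71 | 0.60 | 0.46 | 0.27 |
| ANCOVA | 0.57 | 0.52 | 0.43 | 0.26 |

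For a filter pair (15 v 15) the figures are 0.87, 0.73, 0.57, 0.33 for change and 0.70, 0.63, 0.52, 0.32 for ANCOVA.

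**Step 4: power, 45 v 15, effect 0.8 SD of change** (simulated).

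| Data, k=1 | Test | rho 0.3 | rho 0.5 | rho 0.7 | rho 0.9 |
|---|---|---|---|---|---|
| Normal | Mann-Whitney on change | 72% | 73% | 72% | 72% |
| Normal | t-test on change | 75% | 75% | 75% | 75% |
| Normal | ANCOVA | 90% | 86% | 81% | 76% |
| Heavy tails, t(3) | Mann-Whitney on change | 89% | 89% | 89% | 89% |
| Heavy tails, t(3) | ANCOVA | 91% | 88% | 84% | 80% |

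About 3 points of the normal-data gain over Mann-Whitney come from dropping ranks; the rest is the adjustment.

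With normal data and unequal SDs the pattern over rho changes. At k=1.25, rho 0.7, the t-test on change and ANCOVA both have about 76%. At k=0.8, rho 0.9, Mann-Whitney has about 71% and ANCOVA about 91%.

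With skewed data (lognormal, log-SD 0.5, k=1 on the log scale), Mann-Whitney / raw-scale ANCOVA / log-scale ANCOVA give 78/82/90, 76/76/85, 75/71/81 and 71/64/76% for the four values of rho.

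**Step 5: same question.** ANCOVA of examination 2 and ANCOVA of change, each adjusted for examination 1, give identical group contrasts and P values. Adjustment does not alter what is being compared.

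**Step 6: pairwise filter intervals.** Under the null at rho 0.5, at least one of the three unadjusted pairwise 95% CIs excludes zero in about 12% of trials, against 4.9% for the single Kruskal-Wallis test. Any fix that reports the pairs has to deal with this.

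**The case against.** The strongest defence is that rank tests on change are a legitimate choice in a small trial with unknown distributions. That stands. Both tests hold their level, and with t(3) errors Mann-Whitney matches ordinary ANCOVA at rho 0.5 (89 v 88%) and beats it at 0.9 (89 v 80%). Raw-scale ANCOVA also loses on skewed data at rho 0.7 and above. This is why the rank tests should be kept and not discarded.

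A second objection is that no loss can be asserted, because neither rho nor k is documented. That also stands as to size. A reader might infer that a moderate rho means precision is probably lost, that the gain is material up to rho of about 0.7, or that it is negligible near 0.9. Those thresholds hold only for equal SDs: at k=1.25 and rho 0.7 almost nothing is gained, and at k=0.8 and rho 0.9 the gain is large.

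A reader might also infer from the broken interval sentence that the plan omits any between-group interval. The documents do not support this as a finding. The missing words may have been lost when the PDF was read, and the intended intervals may be on change or on a difference.

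**Conclusion.** The point holds as a precision improvement. A baseline planned for all groups goes unused as a covariate, and using it can reduce the variance by anything from nothing (slope equal to 1) to about half (k=0.8, rho 0.3) over the values examined. At equal SDs the reduction is 35% to 5% as rho goes from 0.3 to 0.9. These sizes rest on assumed rho and k and a linear relation. The power gains further assume roughly normal data, or a suitable scale for skewed data, and can reverse with heavy tails.

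It would be wrong to read this as a claim that Mann-Whitney or Kruskal-Wallis on change is invalid or biased; under randomisation they are not. The incomplete interval sentence is a matter of tidying and carries no weight of its own. Priority: low to moderate.

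**What to change.** For each main outcome (the I/T coefficient for rectangular and for triangular pulses, and PPT):

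1. Prespecify an ANCOVA of examination 2 on group (v, x, y, z) and examination 1. Name the scale, raw or log, in the SAP. Do not let a skewness rule choose it, because chance would then decide between a difference and a ratio.
2. Report the adjusted mean of v, x, y minus z with its 95% CI (as a ratio if the log scale is named).
3. Compare v, x and y by one adjusted test on 2 degrees of freedom. Report the three pairwise filter differences with 95% CIs, but interpret them as significant only if that test gives P<0.05. This deals with the three pairs within an outcome; it does not address multiplicity across the outcomes.
4. Keep Mann-Whitney on change, with a Hodges-Lehmann difference and CI, and Kruskal-Wallis on change as sensitivity analyses.
5. Complete the interval sentence in both SAP paragraphs to match.

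The cost is a few SAP sentences and no new data. The downsides are one degree of freedom, a linear common-slope assumption, and possible loss of power against the rank tests with heavy tails or with skewed data analysed on the raw scale.
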